This study aims to ensure that X-ray images of the pelvis are performed using evidence based protocols. It will also determine if patient posture (erect or supine) has an effect on radiation dose, image quality and diagnostic measures.

[figure not shown]
The study objectives are to:

- Develop trial procedures, imaging protocols and patient information for a future study
- Estimate the recruitment rate for a prospective study which will the diagnostic and dose differences between supine and erect pelvic radiographs
- Identify the recruitment and refusal rates to such research.

Study site

A single NHS Trust is being used to control for variations in technique and equipment. Mid Yorkshire Hospitals NHS Trust (MYH) comprises 3 hospital sites, Dewsbury District Hospital, Pinderfields Hospital (Wakefield) and Pontefract Hospital. Almost 8000 adult patients were referred from either their GP or as an outpatient to the Trust radiology department for pelvis or hip radiographs in 2016, including those referred for a hip x-ray where a full pelvic radiograph is performed as standard. The age profile of these patients is demonstrated in Figure 1. This demonstrates that the median age of this patient population is 65, with 80% of all patients being over 50 years in age.

Method

Phase One: Patient modelling

The initial data collection will focus on ascertaining the patient population and how physical characteristics (body shape) differs between the erect and supine positions. This will be through standardised measures obtained in both positions.

Sample size

A cohort of 180 patients who are attending for radiography of the hip or pelvis from either an outpatient (OP) clinic or their general practitioner (GP) will be recruited. Specifically the study aims to achieve a minimum of 30 patients in each of the following categories:

Underweight/Normal (BMI<25)

Overweight (BMI 25-30)

Obese/Morbidly obese (BMI>30)

Inclusion criteria

All patients who attend for radiographs of the hip or pelvis from a MYH OP clinic or their GP will be eligible for inclusion to the study. It is estimated that there are approximately 60 eligible patients per week attending each hospital site within the study organisation.

Exclusion criteria

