An example of the acquisition procedure is demonstrated in figure 2 below. The resultant images will be analysed for quality in relation to visualisation of the bony anatomy of the pelvis and hip joint. Based on a previously validated technique²⁶ radiation dose (entrance surface dose (ESD) and effective dose (ED)) will be calculated using a commercially available computer software system which utilises Monte Carlo code dose simulation (PCMXC). Calculations require the source-object distance, mAs and peak tube potential values (kV) to be entered for each data point.

Phase Three: Pelvic Radiograph Acquisition

This phase will compare radiographs obtained on the same patient in two different positions, supine and erect. The supine positioning is that which is currently undertaken within the imaging department. The erect positioning technique and acquisition parameters will be informed by the earlier phases of the research.

Sample size

A single arm pilot study is planned with no attempt at this time to undertake sub-group analysis. A minimum of sixty patients will be recruited to this study based on the premise of the future trial demonstrating a 5% difference in pelvic tilt between the 2 projections (95% confidence interval), ²⁷ this exceeds 10% of the potential future trial requirements ^{28,29} and includes a minimum of 12 participants per subgroup. ³⁰

The future trial is estimated to require a minimum sample of 474, based on the same calculations. To allow for the inability to perform the erect x-ray, exclusion based on image quality and to enable sub-group analysis, it is planned that the sample recruited would be 800. The subgroup analysis for referral reason will comprise:

- 1. Young adult with hip pain (18-40)
- 2. Patient with evidence of hip dysplasia
- 3. Older adult referred with symptoms or diagnosis of OA
- 4. Previous hip replacement under monitoring

Inclusion criteria

All patients who attend for general radiography of the hip or pelvis from their general practitioner or outpatient clinic will be eligible for inclusion to the study. It is estimated that there are approximately 60 eligible patients per week attending any one hospital site within the study organisation.

Exclusion criteria

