Appendix 3. Phase 1: Data collection instructions

A study to compare supine and erect pelvis radiographs – assessment of impact on radiation dose and diagnostic markers (SEPRAIDD)

Preparation

Patient will have been greeted by a GCP trained radiographer who will introduce themselves and explain the study, prior to obtaining consent. If consent is gained then the patient will complete paperwork and be asked to change in to a gown as required for their examination.

If the examining radiographer is different to the one obtaining consent repeat ID checks should be undertaken following introduction of self. Confirmation of participant agreement to proceed should be sought verbally.

Study procedure

Height and Weight should be undertaken on the study calibrated weigh scale, in cm and kg.

A disposable 150cm tape measure should be used to measure body circumference at the levels of the lower costal margin, the iliac crests and the greater trochanter. Source-patient distance will be measured using the built in tape measure on the x-ray tube within the room.

- 1. The patient should be positioned AP against the erect bucky. The tape is passed around their body, the appropriate landmark palpated ensuring that the tape is parallel to the floor. The measurement should be taken whilst the patient is in arrested expiration and recorded on the data collection sheet. This is repeated for all three anatomical levels.
- 2. The patient should be asked to remain in the same standing position whilst the tube head is positioned at 115cm SID. The light beam is used to centre the tube at the level of the iliac crests. Measurements are taken, using the built in tape measure at the tube head, in the midline at the level of the lower costal margin, iliac crests and greater trochanters (to correlate with tape measure circumference readings). Arrested expiration should again be utilised.

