Appendix 7. Phase 3: Data collection sheet

A study to compare supine and erect pelvis radiographs – assessment of impact on radiation dose and diagnostic markers (SEPRAIDD)

Study ID Number:			Imaging order
Patient Hospital Number:			
Height:	m _	Weight:	kg
Age:		Gender:	M / F
Supine radiograph Start time:	Repe	at Yes/No	
kV	kV _		
mAs	mAs		
DAP	DAP		
EI Image time:	EI		
Erect radiograph Start time:	Сог	nments:	
kV			
mAs			
DAP			
EI Image time:			
Patient preference			
Supine / Erect			

Radiographer code:

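### Phase one infers body diameter from tube-to-skin distance without measuring the surface-to-receptor gaps, so any table-wall gap difference enters the erect-supine change; room should also be recorded, and held fixed per patient in phase three

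*Protocol*

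**What the plan says.** **Phase one measurement.** Under Phase One, Data collection, the distance from tube to skin is taken as a stand-in for body diameter. Appendix 3 gives the procedure: "Source-patient distance will be measured using the built in tape measure on the x-ray tube within the room". In step 2 the patient stands at the erect bucky with the tube at 115 cm SID. In step 3 the patient lies on the table with the tube again at 115 cm SID. Readings are taken at the lower costal margin, iliac crests and greater trochanters, and circumference is taped at the same three levels in both postures. No step reads the distance to the empty table top or empty bucky face. Phase Two then alters the phantom according to the mean differences between positions found in phase one.

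**Control of equipment.** The Study site section says: "A single NHS Trust is being used to control for variations in technique and equipment". It then says that the Trust "comprises 3 hospital sites, Dewsbury District Hospital, Pinderfields Hospital (Wakefield) and Pontefract Hospital". Phase one eligibility covers the whole Trust: "All patients who attend for radiographs of the hip or pelvis from a MYH OP clinic or their GP will be eligible for inclusion". Phase three names no hospital and gives its volume as "approximately 60 eligible patients per week attending any one hospital site within the study organisation".

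**What is recorded.** The Appendix 4 sheet has no field for site, room or operator. The Appendix 7 sheet has a field for "Radiographer code" but none for site or room.

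**Phase three comparison.** The design is paired: "This phase will compare radiographs obtained on the same patient in two different positions, supine and erect". Study procedures fix the two SIDs and randomise the order of positions. They do not mention room or tube.

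**The concern.** SID runs from the source to the image receptor, which lies some way behind the surface that the patient touches. With SID held at 115 cm, a tube-to-skin reading therefore reflects body thickness plus that hidden depth. The table and the wall bucky are different assemblies, and their depths need not be equal. If they differ, part of the apparent change in body shape between standing and lying is a property of the furniture. The mean change shapes the phantom, the phantom yields the exposure settings, and phase three uses those settings, so an error here can travel through all three phases.

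The second matter is smaller. Using one Trust limits variation compared with using several, but it does not by itself hold equipment constant across three hospitals and their rooms. Without a site or room field, nobody could check from the planned data whether the gap error or the supine-erect difference varies by room.

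**Working it through.** The plan states no figure on this point, so there is none to reproduce. The first check is geometric and the second is an illustration.

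**1. Gap term in phase one**

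Inputs:
- SID = 115 cm in both postures (Appendix 3, steps 2 and 3).
- S_e and S_s: tube-to-skin readings, erect and supine (Appendix 4).
- g_w and g_t: depth from bucky face to receptor and from table top to receptor. Neither is measured, and no value is in the documents.

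At a given level, with the patient touching the surface and the reading taken perpendicular to the receptor:
- Erect thickness: T_e = 115 − g_w − S_e
- Supine thickness: T_s = 115 − g_t − S_s
- True change: T_e − T_s = (S_s − S_e) + (g_t − g_w)

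The recorded data supply only S_s − S_e. The error in the inferred change is therefore

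(S_s − S_e) − (T_e − T_s) = g_w − g_t.

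For an assumed absolute gap difference of 1, 2 or 4 cm, the error is 1, 2 or 4 cm, at all three levels and in every patient measured in that room. Its sign depends on which gap is larger.

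- *Pairing:* the term is a difference between the two halves of the pair, so pairing does not cancel it.
- *Sample size:* averaging the same constant over 180 patients returns that constant. With several rooms, the mean error is the average of the room-specific differences, weighted by patients per room.
- *Subgroups:* when BMI, gender or age groups measured in the same room are compared, the constant cancels. It is the mean change itself that is affected.

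With an empty-surface reading E = 115 − g for each surface, thickness is E − S. The change is then (E_w − S_e) − (E_t − S_s), which equals T_e − T_s exactly, and the gap term is gone.

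**2. Room differences in phase three**

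*Does the described pool cover all three hospitals?* Study site gives almost 8000 referrals a year: 8000 / (52 × 3) = 51.3 per site per week, roughly in line with the stated 60. The pool described is Trust-wide. This does not show that all three sites will recruit.

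*What could a room difference do?* Let R be the ratio of a measured dose quantity between two rooms, and q the share of patients whose erect image is made in the higher-reading room and supine image in the other, with no patients split the opposite way. On the log scale the paired comparison gives

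bias in the erect/supine ratio = R^q − 1.

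All values of R and q are assumed:

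| R | q = 0 | q = 10% | q = 25% | q = 50% |
|---|---|---|---|---|
| 1.1 | 0% | 1.0% | 2.4% | 4.9% |
| 1.2 | 0% | 1.8% | 4.7% | 9.5% |
| 1.3 | 0% | 2.7% | 6.8% | 14.0% |

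If equal shares are split in each direction, the net exponent is zero and the bias is R^0 − 1 = 0; only extra variance remains. If both images are made in one room, a constant room ratio cancels.

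**The case against.** **On the gap.** The protocol calls the distance a proxy and gives no formula for turning it into a diameter, so the conversion could be set out in an analysis plan that is not shown. That is fair as far as the formula goes. But an analysis cannot subtract a depth that was never measured, and a later look-up of room geometry would need the room, which Appendix 4 does not record. Circumference is taped in both postures at the same levels and does not depend on any gap. This stands as a real cross-check: the tube distance is not the only information on body shape. It does not correct the distance readings themselves. It might also be said that the gap error could be as large as the anatomical change. The documents give no anatomical change, so that comparison cannot be made.

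**On equipment.** A reader might infer that equipment differences contaminate the supine-erect comparison generally. The documents do not support this:
- Phase one is written as one sequence in one x-ray room, so a same-room complaint does not apply there.
- Phase three is paired, nothing suggests moving a patient between rooms, and bias would need a systematic split.
- Recruitment at all three hospitals is permitted but not stated. Ethical Consideration refers in passing to a single study site.
- A difference in tube output does not pass straight into calculated dose, because ESD and ED are computed from kV, mAs and source-object distance. It could show in DAP, or in mAs under automatic exposure control.
- Both sheets carry the hospital number and the images are kept on PACS, so site may be traceable, although identifiers are removed at transcription and no such step is planned.
- A limited group of trained radiographers and continuing image checks serve the technique part of the stated control.

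**Conclusion.** The point stands for phase one. Followed as written, Appendix 3 places any table-wall difference in surface-to-receptor depth into the mean erect-supine change in inferred diameter, in full and in every patient measured in that room. Its size is unknown: 1-4 cm is an assumption, and it would be zero in a room where the two gaps happen to be equal. The conclusion also assumes that 115 cm is set to the receptor and that readings are perpendicular to it.

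The equipment point is secondary. One Trust with three hospitals does not by itself control for equipment, and the sheets would not show a room effect. Harm to the phase three comparison is conditional: bias if patients are split across rooms systematically, added noise if they are split haphazardly, and none from a constant room ratio if each patient stays in one room.

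Overall this is a cheap improvement of minor to moderate severity in a pilot. It matters somewhat more because developing procedures for a future study is one of the stated objectives.

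**What to change.** 1. In Appendix 3, add a one-off step for each room used: with the tube at 115 cm SID, read the built-in tape to the empty table top and to the empty erect bucky face. Take body diameter as that reading minus the tube-to-skin reading.
2. Add site and room to the sheets in Appendices 4 and 7.
3. In Phase Three, Study procedures, state that both exposures of a patient are made in the same room.
4. In Study site, either name the hospitals and rooms to be used, or say that a single Trust limits equipment variation rather than controls for it.

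The cost is two tape readings per room, two extra fields per sheet and one or two sentences. No extra patients or exposures are needed. The one practical drawback is that a phase three patient may occasionally wait for a room with both the table and the erect bucky free.

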The recruited participant will be asked to change into a gown appropriate to their radiological examination and then taken to a private room (x-ray room) to maintain dignity and privacy. They will then have various measures undertaken by the research team member (see instruction sheet appendix 3).

These will include:

- Height (m)
- Weight (kg)
- Body circumference
- Source-Object Distance (i.e. x-ray tube to patient skin, as a proxy for body diameter)

A small group of radiographers will be trained to undertake the specific study parameters to ensure consistent data collection (Appendix 4). They will then continue with the radiographic examination as requested by the referring clinician.

Data analysis

The data collected will allow modelling of the change in patient body shape between the two projections. Variations in shape between BMI subgroup, gender and age will be assessed. Mean and standard deviations will be calculated if the resultant data are approximately normally distributed and median (ISR) measures will be determined for non-parametric data.

[figure not shown]
Phase Two: Phantom Experiment

An anthropomorphic phantom of the abdomen and pelvis will be used to investigate the optimal image acquisition protocol based on the anatomical changes identified in phase one. No patients will be recruited for this part of the study.

The outcome of the phantom study will be specific kV and mAs settings or automatic exposure control (AEC) settings for the different techniques and comparison of the phantom dose data with national diagnostic reference levels.

Based on the variation in mean measures between the different position and body habitus in phase one a Kyoto phantom will be physically altered with the addition of appropriately positioned soft tissue density mimicking material. This will enable multiple exposures of the phantom to be made at different distances and exposure factors to ascertain whether automatic exposure devices can be reliably used in both of the patient positions or whether specific exposure charts should be calculated regarding a patient's body habitus.

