- 3. The patient is then asked to lie on the bucky table which is then set at its normal height. Tape measurements of body circumference are again made at the same three levels, this time ensuring that the tape measure remains perpendicular to the table top. The tube head is placed at 115cm SID, above the patient, and centred in the midline at the level of the lower costal margin. The built in tape measure at the tube head should be used to take a measurement at the level of the lower costal margin. The floating table top is then used to repeat these measurements centred over the iliac crests and greater trochanters.
- 4. The patient should then be thanked for their cooperation and their radiographic examination is undertaken.
- 5. The tape measure should be disposed of following completion of the examination.

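### In phase one the tube-to-skin proxy for body diameter carries the difference between the table and erect-stand receptor gaps into the erect–supine change, and nothing is recorded to remove it

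*Protocol*

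**What the plan says.** The protocol's phase one data collection list includes "Source-Object Distance (i.e. x-ray tube to patient skin, as a proxy for body diameter". No formula for turning that reading into a diameter is given.

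Appendix 3 sets out the readings:

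- Erect: "The patient should be positioned AP against the erect bucky", and then "The patient should be asked to remain in the same standing position whilst the tube head is positioned at 115cm SID".
- Supine: "The patient is then asked to lie on the bucky table which is then set at its normal height", and then "The tube head is placed at 115cm SID, above the patient".
- Instrument: "Source-patient distance will be measured using the built in tape measure on the x-ray tube within the room".

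The Appendix 4 sheet takes a source-centring distance and a tape circumference at three anatomical levels in each posture, with height, weight, age, gender and two identifiers. It has no field for the distance from tube to table top or bucky face, for the surface-to-receptor gap, or for the room or site.

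The phase one analysis uses these data to model how body shape changes between positions. Phase two then acts on the result: "Based on the variation in mean measures between the different position and body habitus in phase one a Kyoto phantom will be physically altered".

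**The concern.** A tube-to-skin distance at fixed SID tells us body thickness only if we also know how far the supporting surface lies in front of the receptor. That gap belongs to the equipment. Every erect reading is taken on one type of device and every supine reading on another, so a difference between their gaps cannot be separated from a difference between postures. It enters as a constant shift in the paired change, at all three levels.

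The paired change is what phase one exists to estimate, and its mean guides how much soft-tissue material is added to the phantom. If the gaps differ, some equipment geometry could be built into the phantom as tissue, or could hide real tissue. Exposure settings or charts worked out on that phantom would inherit the error.

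**Working it through.** The plan states no figure for this quantity, so there is none to reproduce. The check is geometric. It takes SID in its usual sense (source to image receptor) and assumes perpendicular readings.

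**Inputs from the protocol:** SID = 115 cm in both postures (Appendix 3, steps 2 and 3); phase one n = 180, with at least 30 per BMI category (phase one, Sample size).

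**Inputs not in the protocol:** body thickness T, surface-to-receptor gap g, and the SD of the paired change. All values used for these are assumptions, for illustration only.

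**Identity.** SID = SSD + T + g, where SSD is the tube-to-skin distance.

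**Change inferred from SSD at equal SID.**

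SSD(supine) − SSD(erect) = [T(erect) − T(supine)] + [g(erect) − g(table)]

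The second bracket is the bias.

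**Example, table gap larger.** Assume T = 22 cm supine and 24 cm erect, with gaps of 7 cm (table) and 5 cm (stand).

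- Supine SSD = 115 − 7 − 22 = 86 cm.
- Erect SSD = 115 − 5 − 24 = 86 cm.
- Inferred change = 86 − 86 = 0 cm, against a true change of +2 cm.

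**Example, gaps reversed** (table 5 cm, stand 7 cm).

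- Supine SSD = 115 − 5 − 22 = 88 cm.
- Erect SSD = 115 − 7 − 24 = 84 cm.
- Inferred change = 88 − 84 = +4 cm, against the same true +2 cm.

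**Range, with a true change of +2 cm.**

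| g(erect) − g(table), assumed | Inferred change |
|---|---|
| −4 cm | −2 cm |
| −2 cm | 0 cm |
| 0 cm | +2 cm |
| +2 cm | +4 cm |

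**Comparison with sampling error.** The 95% half-width for a mean paired change is 1.96 × SD / √n.

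- SD 2 cm (assumed): 1.96 × 2 / √180 = 0.29 cm; at n = 30, 0.72 cm.
- SD 3 cm (assumed): 0.44 cm at n = 180; 1.07 cm at n = 30.

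Under these SDs a gap difference of 1 cm exceeds the sampling half-width in every case except SD 3 cm at n = 30. The half-width shrinks as n grows; the offset does not.

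**Subtracting empty readings (first example).** With no patient, source to table top = 115 − 7 = 108 cm and source to bucky face = 115 − 5 = 110 cm. Thickness is 108 − 86 = 22 cm supine and 110 − 86 = 24 cm erect. The change is +2 cm, as it should be.

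**The case against.** The strongest reply is that the bias has no demonstrated size. Neither gap is in the documents, and equal gaps would cancel. This stands: the geometry shows a route for bias, not an amount or a direction.

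Second, a gap is a fixed property of the equipment, so it could be measured later and subtracted, perhaps under a working instruction or analysis plan not shown. This stands in part. It requires knowing which room each patient was measured in, which the sheet does not record. The hospital number might allow the room to be traced through the imaging record, but the protocol does not provide for that.

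Third, tape circumference is taken at the same levels in both postures and does not depend on the gaps, and the phantom is altered from several measures. That is a real partial check, but circumference is not AP thickness and does not fix how much material belongs in the beam path.

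Fourth, a constant gap within a room leaves contrasts between BMI, gender and age groups intact. This is correct; the mean posture change is what is exposed.

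A reader might go further and infer that phase three exposures will be wrong by some calculable factor. The documents do not support that. It would need a gap difference and a half-value layer, neither of which is given. Phase two is also to test whether automatic exposure control is reliable in both positions, and if it is adopted, exposure would respond to the actual patient. Phase three adds height and weight to confirm the parameters, and the ethics section provides image-quality review and dose monitoring.

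A reader might also infer that equipment at all three hospitals is mixed in phase one. The Study site section says that the Trust has three sites, not that phase one uses all of them. The bias needs only one room with two devices.

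**Conclusion.** The point holds as a limitation of the measuring instructions. As written, the erect–supine change in the diameter proxy equals the true change in AP thickness plus the erect-stand gap minus the table gap, and the sheet holds nothing with which to separate them. The bias is zero if the gaps are equal and otherwise equals their difference, centimetre for centimetre, in either direction and at any sample size. Its actual value cannot be taken from the documents.

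The consequence is confined to the mean posture change and the phantom build that follows from it, and bears mainly on fixed exposure settings or charts. The raw tube-to-skin distance remains the right input for the dose calculation, which needs the actual source-object distance.

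**What to change.** In each room used for phase one, with no patient present and the tube at 115 cm SID, read once:

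1. source to table top, with the mattress in place if one is used;
2. source to the face of the erect bucky.

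Add a room code to the Appendix 4 sheet. State in the protocol that AP thickness in each posture is the empty reading for that room and posture minus the patient's tube-to-skin reading, and use that thickness for the phase one change and the phantom build. Keep the raw tube-to-skin distance for the dose calculation.

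The cost is two tape readings per room, one extra field and one subtraction in the analysis. It adds no patient burden and no exposure.

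### The claim that the phase three sample includes at least 12 participants per subgroup is not secured by the design

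*Protocol*

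**What the plan says.** Protocol, Phase Three, Sample size: "A minimum of sixty patients will be recruited to this study". Three supports follow: a premise about pelvic tilt in the future trial, a total above 10% of that trial's requirement, and the statement that the sample "includes a minimum of 12 participants per subgroup". The paragraph opens with "A single arm pilot study is planned with no attempt at this time to undertake sub-group analysis".

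The next paragraph puts the future trial at a minimum of 474, with 800 planned, partly to allow subgroup analysis. It then lists four groups under "The subgroup analysis for referral reason will comprise": adults aged 18 to 40 with hip pain, "Patient with evidence of hip dysplasia", older adults with OA symptoms or diagnosis, and monitored hip replacements. No other subgroups are named for phase three, so I take the 12 to refer to these.

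Phase Three, Inclusion criteria: "All patients who attend for general radiography of the hip or pelvis from their general practitioner or outpatient clinic will be eligible". The Phase Three recruitment process sets no quota, cap or subgroup target. Phase One, by contrast, states an aim of at least 30 patients in each of three BMI categories.

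Study site, on adult GP and outpatient referrals in 2016: "This demonstrates that the median age of this patient population is 65, with 80% of all patients being over 50 years in age".

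Appendix 7 (phase three data sheet) records age, sex, height, weight, exposure data and preference. It shows no field for referral reason.

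**The concern.** The clause describes a property of the sample, and it serves as one of the reasons for choosing 60. Four groups of 12 fit inside 60 only if recruitment is steered towards the smaller groups, and nothing in phase three steers it. The clause also sits oddly beside a statement, in the same paragraph, that subgroups will not be analysed.

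What is at stake is how the pilot is read later. The increase from 474 to 800 is partly for subgroup analysis. A reader planning that trial could believe the pilot supplies at least 12 patients in each group when it may not, and the data sheet as shown would not reveal the shortfall.

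**Working it through.** **Reproducing the plan's figures.** 10% of 474 = 47.4, which is below 60. 4 × 12 = 48, which is also below 60, and an equal split would give 60/4 = 15 per group. As totals these are consistent.

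**Inputs.** n = 60 and the minimum of 12 (Phase Three, Sample size); recruitment open to all eligible attenders (Phase Three, Inclusion criteria); 80% of attenders over 50 (Study site), hence 20% aged 50 or under. The 18 to 40 share is not stated in the text available (Figure 1 is not shown), and no share with dysplasia is given anywhere.

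**One group.** If a group makes up a share p of recruits and patients are taken as they come, the number X among 60 is binomial:

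P(X ≥ 12) = Σ (k = 12 to 60) C(60, k) p^k (1 − p)^(60 − k)

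| Share p | Expected of 60 | P(at least 12) |
|---|---|---|
| 25% | 15.0 | 0.852 |
| 20% | 12.0 | 0.551 |
| 17.5% | 10.5 | 0.355 |
| 15% | 9.0 | 0.181 |
| 14% | 8.4 | 0.126 |
| 10% | 6.0 | 0.015 |

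A share of about 24% is needed for an 80% chance of 12, and about 26% for a 90% chance.

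**Young adults.** The 20% row counts everyone aged 50 or under, so it overstates the 18 to 40 group with hip pain. Spreading the 20% evenly over ages 18 to 50 gives about 0.20 × 23/33 = 14%. That is an assumption, and the 15% and 10% rows show the range around it. Without steering, a 90% chance of 12 would need 81 patients at a 20% share, 108 at 15% and 164 at 10%.

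**All four groups at once.** Treating the groups as disjoint and exhaustive, I simulated multinomial samples of 60 (400,000 draws). The chance that every group reaches 12 is:

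- 25/25/25/25%: 0.46
- 20/20/30/30%: 0.23
- 20/10/40/30%: 0.004

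Equal shares are the most favourable split for disjoint groups. They are also hard to square with the Background section, which makes OA the largest non-trauma use of hip radiography. The unequal splits are illustrations, not documented shares.

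**Dysplasia.** With no documented share, no probability can be attached to this group.

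**The case against.** Several points on the other side stand.

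- There is no arithmetic error: 48 fits within 60. The issue is whether the design delivers the stated minimum.
- A reader might infer that the age profile makes 12 patients with dysplasia very unlikely. It does not. The dysplasia group has no age limit, and the Background says hip radiographs assess dysplasia and other pathology at all ages.
- The 20% describes all adult GP and outpatient referrals in 2016, not phase three recruits. Excluding people who cannot stand unaided, or who have had recent trauma, surgery or pelvic imaging, may remove more older patients and raise the younger share. The shift would have to be large. Starting from 14%, reaching even 20% (0.14/0.20 = 0.70 of attenders left, 0.56 of them from the other 0.86) would mean excluding about 35% of everyone else and no young adults.
- Sixty is a floor, so recruitment could continue. But no rule says that it continues until the groups fill.
- The groups overlap (a young adult may have dysplasia), which makes 12 in each easier to reach. The joint figures are therefore illustrative; the single-group figures are unaffected.
- The clause could be read as a recruitment requirement. Phase One words its category minimum as an aim; phase three has no such wording.
- Referral reason may be recoverable through the hospital number on the sheet, or from the screening questionnaires mentioned under Ethical Consideration. The gap on the sheet shows only that the group is not recorded there.
- No pilot subgroup analysis is planned, so no stated output fails. The stated objectives concern procedures, recruitment and refusal.

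**Conclusion.** The statement is wrong as written: it asserts a property of the sample that the phase three design does not secure. Under the favourable assumption of four equal, disjoint and exhaustive groups, the chance that 60 unselected patients meet it is about 46%. For adults aged 18 to 40 it is unlikely to be met: 55% at a ceiling that counts everyone up to 50, about 13% to 18% at shares of 14% to 15%, and 1.5% at 10%. These figures assume exactly 60 patients taken as they come. Shares below 20% are assumptions, and the phase three age mix may differ from that of 2016 attenders. For dysplasia the documents support only that the minimum is not secured.

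A reader might go further and infer that 60 is too small or that the pilot's purpose fails. The documents do not support that. The comparison with 10% of 474 does not depend on the clause, and no subgroup result is promised.

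**What to change.** Delete the clause on 12 participants per subgroup. State that n=60 rests on the overall justification (60 against 47.4, which is 10% of the 474 minimum) and that the pilot gives overall estimates only. That agrees with the paragraph's own opening. Tie the 10% explicitly to 474, because 10% of the planned 800 would be 80.

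Add a referral subgroup field to the Appendix 7 sheet, allowing more than one group or none, so that the counts achieved can be reported when the future trial is planned.

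The cost is one deleted clause, one added sentence and one extra field; sample size and recruitment do not change. Subgroup quotas are not needed for this: turning away eligible patients could distort the recruitment rate that the study sets out to estimate.
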